not limited to: allogeneic organ transplant (e.g., solid organ, bone marrow, or stem cells); cardiac disease (e.g., unstable angina, myocardial infarction, ventricular arrhythmia); congestive heart failure; liver disease; neurological disease; hematological disease; kidney disease; uncontrolled seizure disorder; uncontrolled pulmonary disease; uncontrolled gastrointestinal disease; uncontrolled endocrinological disease; uncontrolled psychiatric disease; or uncontrolled diabetes mellitus

14. Has interstitial lung disease requiring the use of supplemental oxygen
15. Has received or is expected to receive any live viral or bacterial vaccination within 3 months prior to Screening
16. Has received a Bacille Calmette-Guerin (BCG) vaccination within 12 months of Screening or is expected to receive it during the course of the study
17. Has a history of or ongoing active, chronic, or recurrent infection (including bacterial, viral, parasitic, protozoal, and/or fungal/granulomatous infections [e.g., histoplasmosis, coccidioidomycosis, aspergillosis]) requiring treatment with systemic antimicrobials, antivirals, antiparasitics, antiprotozoals, or antifungals within 12 weeks prior to Screening, or serious infection (including but not limited to pneumonia, sepsis, bone or joint infection) requiring hospitalization or treatment with IV antibiotics within 12 weeks prior to Screening
18. Has a history of opportunistic infection or non-tuberculosis mycobacterial infection within 9 months prior to Screening
19. Has any other condition that would, in the opinion of the Investigator, potentially compromise the safety or compliance of the patient or preclude the patient's successful completion of the study

Number of Patients:

Approximately 36 patients will be randomized to the three following cohorts in a 1:1:1 ratio:

- Once weekly SC injections of placebo (Sterile Saline for Injection, USP/EP)
- Once weekly SC injections of IMO-8400 at 0.6 mg/kg
- Once weekly SC injections of IMO-8400 at 1.8 mg/kg

Investigational Product, Dosage and Mode of Administration:

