- Serum samples for presence of autoantibodies associated with idiopathic inflammatory myopathies, including, but not necessarily limited to, the following: anti-MDA-5, anti-Mi-2, anti-TIF1 γ , anti-NXP2, anti-SAE1, anti-SAA 60, anti-Ro/SSA 52, anti-SSB/La, anti-Sm, anti-RNP, anti-Scl-70, anti-ribosomal-P, anti-chromatin, anti-Jo-1, anti-PL-7, and anti-PL-12.

Immunogenicity:

- Serum samples for antibodies to IMO-8400 and antibodies to double-stranded deoxyribonucleic acid (dsDNA)

Statistical Methods

Determination of Sample Size

This study has approximately 80% power to detect a difference of 7 points in change from baseline on the mCDASIV2-Activity score at Week 25 using a 1-sided test with an alpha of 0.05.

Randomization

Randomization will be performed centrally in a 1:1:1 ratio (placebo or IMO-8400 at 0.6 mg/kg or 1.8 mg/kg) and will be stratified by baseline CDASIV2-Activity score (15 to 20 vs. \geq 21).

Analysis Populations

- Safety Population and Intent-to-Treat Population (ITT): All patients who received at least 1 injection of study medication
- Per Protocol Population (PP): All patients who received at least 20 doses of study drug as assigned, completed the EOT Visit 26/Week 25, and had no major protocol violations that would potentially influence treatment effect (as determined by review by Idera prior to unblinding)

Safety analyses will be performed using the Safety Population. The efficacy, PD, disease-specific autoantibodies, and immunogenicity assessments will be analyzed for the ITT population; key endpoints may be also analyzed for the PP Population as specified in the Statistical Analysis Plan (SAP).

Primary Safety and Tolerability Endpoints

- Number of patients discontinuing treatment due to AEs

- Frequency and severity of AEs
- Physical examination findings, including vital signs
- Standard laboratory safety tests including hematology, chemistry, coagulation and urinalysis
- Assessment of ISRs
- ECG findings
- Laboratory safety assessments including CH50, C3, C4, troponin, CRP, albumin, globulin, A:G ratio, proteinuria, eGFR, and platelet count

Primary Efficacy Endpoint

- Change from baseline in mCDASIV2-Activity score

Safety Analyses

Adverse events will be coded using the Medical Dictionary for Regulatory Activities (MedDRA) and tabulated by event, grade, and relationship to study therapy. Safety analyses will be descriptive in nature; no statistical hypothesis testing will be performed.

Efficacy Analyses

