14.2 Determination of Sample Size

A simulation was conducted in which one of the IMO-8400 groups exhibits a mean decrease of 7 points in CDASIV2-Activity score over 24 weeks, assuming a baseline mean of 25 and a standard deviation of 8.5 and the placebo group exhibits no mean decrease. Correlation between baseline CDASIV2-Activity score and Week 25 mCDASIV2-Activity score was assumed to be 0.4 for IMO-8400 treated patients and 0.7 for placebo treated patients. Using a repeated measures mixed model (RMMM) to analyze monthly mCDASIV2-Activity assessments, 10 patients with complete data yields 81.2% power to detect such a 7-point difference between groups at Week 25, using a 1-sided test with an alpha of 0.05. A 20% rate of patient dropout was assumed, yielding the final sample size of 12 subjects per treatment group.

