14.4.4 Efficacy Analyses

The primary efficacy endpoint will be assessed via an RMMM. An appropriate covariance structure for repeated measures will be used. The difference between each IMO-8400 treatment group and placebo at Week 25 will be assessed. The overall alpha level will be controlled using the Bonferroni-Holm step-down method. Further details of this analysis will be described in the SAP. A sensitivity analysis will be performed to test the effect of important covariates on the effect of IMO-8400 using an RMMM.

Differences in response rate between the IMO-8400 treatment groups and placebo will be assessed via logistic regression.

The MMT8, TUG, 4 stair climb test, timed 10MWR test, serum CK, ALD, LDH, AST, ALT, SF-36, and 5-D Itch Scale will be analyzed in a similar manner to the primary endpoint.

For the proportion of patients who meet the IMACS 2004 DOI (Rider 2004) at EOT, logistic regression will be performed.

All efficacy endpoints will also be summarized descriptively by treatment group and nominal visit. Other exploratory and sensitivity analyses will be specified in the SAP in addition to further details regarding the statistical methodology.

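### Section 14.2: 12 per group at the stated 20% dropout leaves 9.6 expected completers, not the 10 on which the 81.2% power rests

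*Protocol*

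**What the plan says.** Section 14.2 reports a simulation in which "one of the IMO-8400 groups exhibits a mean decrease of 7 points" and placebo shows no mean change. It concludes that "10 patients with complete data yields 81.2% power to detect such a 7-point difference between groups at Week 25"; the test there is one-sided at the 0.05 level. The step from evaluable to randomised patients is one sentence: "A 20% rate of patient dropout was assumed, yielding the final sample size of 12 subjects per treatment group". How 12 was obtained is not explained.

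The synopsis carries this forward: "Approximately 36 patients will be randomized to the three following cohorts in a 1:1:1 ratio", and "This study has approximately 80% power to detect a difference of 7 points in change from baseline".

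For the analysis, Section 14.4.4 says: "The difference between each IMO-8400 treatment group and placebo at Week 25 will be assessed". It adds: "The overall alpha level will be controlled using the Bonferroni-Holm step-down method".

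**The concern.** An allowance for dropout should make the expected number of completers equal the number on which power was calculated. With 12 randomised and 20% lost it does not. This is the only justification the protocol gives for its 36 patients, and no other section corrects it.

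A second mismatch comes into view once the power has to be restated. The 81.2% belongs to a single dose-placebo comparison at the full one-sided 0.05. The planned analysis tests two doses with Holm control, so a dose must pass 0.025 unless the other dose has already done so. Correcting the completer count alone would still leave a power figure for a test that is not the planned one.

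**Working it through.** **Inputs (Section 14.2):** 10 completers per group; power 81.2%; difference 7 points; one-sided alpha 0.05; dropout 20%; 12 per group. From Section 14.4.4: two comparisons with placebo, Bonferroni-Holm.

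**1. Reproducing the 12.** 10 x (1 + 0.20) = 12, exactly the stated figure. Multiplying by one plus the dropout rate, instead of dividing by one minus it, is the likely origin, though the protocol does not say so.

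**2. The dropout arithmetic.**
- Expected completers from 12: 12 x (1 - 0.20) = 9.6.
- Number needed to keep 10: 10/(1 - 0.20) = 12.5, so 13 per group and 39 in total.
- Dropout at which 12 keeps 10: 1 - 10/12 = 16.7%.
- Chance that a group keeps at least 10 completers at 20% dropout (binomial): 55.8% with 12, 74.7% with 13.

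**3. Effect of the slip on power, taking 81.2% as given.** On the normal scale the implied noncentrality is z(0.812) + z(0.95) = 2.530, so SE = 7/2.530 = 2.77 (2.66 with a t reference on 18 df). Scaling to 9.6 completers:
- 2.530 x sqrt(9.6/10) = 2.479, and Phi(2.479 - 1.645) = 79.8% (79.7% with t).
- Averaged over independent Binomial(12, 0.8) completer counts in both arms: 79.1% (78.9% with t).
- If dropouts' earlier visits enter the mixed model (seven visits, linear or categorical time, exchangeable or AR(1) covariance, anchored to 81.2%): 80.0-81.6% if all dropouts leave straight after baseline, 81.2-83.5% if departures are spread evenly.

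**4. Effect of the Holm step, same anchor.** At the first-step level of 0.025, Phi(2.530 - 1.960) = 71.6% with 10 completers and Phi(2.479 - 1.960) = 69.8% with 9.6 (70.2% and 68.2% with t on the two-arm df). A three-arm simulation of the full procedure, with the shared placebo arm, gives:

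| Scenario | 10 completers | 9.6 completers |
|---|---|---|
| One dose effective, other assumed zero: power for the effective dose | about 72% | about 70% |
| Both doses at 7 points: power for a given dose | about 77-78% | about 76% |
| Both doses at 7 points: at least one dose significant | about 85% | about 84% |

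**5. Can the 81.2% itself be reproduced?** Not uniquely, because the protocol gives neither the intermediate-visit correlations nor the form of the mixed model. Assuming SD 8.5 at Week 25 as well, with 10 per group:
- Change score: SE = sqrt[(2 x 8.5^2 x 0.6 + 2 x 8.5^2 x 0.3)/10] = 3.606, power 58.8% (t) to 61.6% (normal).
- Baseline-adjusted with arm-specific slopes: SE = sqrt[8.5^2 x (0.84 + 0.51)/10] = 3.123, power 69.2% to 72.5%.
- Linear-time exchangeable mixed model: about 75% to 85%.

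The stated 81.2% is therefore reachable, and nothing here shows it to be wrong. The spread is a reason to confirm that the re-run tests the Week 25 contrast actually planned.

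**The case against.** The strongest reply is that the shortfall is 0.4 of a patient per group. Power moves from 81.2% to just under 80%, and the synopsis promises only about 80% and about 36 patients, so both statements survive. The planned mixed model (Section 14.4.4) is run on everyone dosed (Section 14.3) without imputation (Section 14.6), and early leavers are asked to attend a termination visit with the end-of-treatment assessments (Section 10.1.4). Counting completers therefore probably overstates the loss, and power may not fall at all. All of that stands as to size. It does not rescue the text, because Section 14.2 ties its power to patients with complete data and links 10 to 12 through the dropout rate. If partial data were meant to close the gap, the section should say so.

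A second reply is that the Holm point is a different issue, that the 68-72% figures depend on a zero effect for the second dose, and that the chance of at least one significant dose exceeds 81.2% when both work. It is right that those lower figures come from multiplicity and not from dropout, and the favourable scenario belongs in the account, which is why it is tabulated above. But a single effective dose is the case Section 14.2 itself simulates, and both the simulated test and the Holm plan are stated in this protocol.

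**Conclusion.** The concern holds. At the protocol's own dropout rate, 12 per group gives 9.6 expected completers, and the number that preserves 10 is 13 per group.

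The slip alone costs about 1.4 points of power at the expected completer count (about 2 points averaged over random dropout) if only completers count, and possibly nothing if partial data are used. It does not make the trial materially underpowered or require more patients.

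The larger gap is between the stated power and the planned test. With the Holm step and 9.6 completers, power for a given 7-point dose is about 68-70% if the other dose has no effect and about 76% if both doses have the effect. The chance of at least one significant result in the latter case is about 84%.

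These figures take the 81.2% as correct, back-calculate the standard error from it, and assume the second dose's effect, which the protocol does not state.

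**What to change.** Keep 36 patients. In Section 14.2, replace the dropout sentence with wording such as: With 12 patients per group and 20% dropout, 9.6 per group are expected to have complete data; 12 per group retains 10 if dropout is at most 16.7%.

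Re-run the simulation with 12 randomised per group and 20% dropout, for the Week 25 contrast of Section 14.4.4 including its Bonferroni-Holm step. State the effect assumed for the second dose, whether visits before dropout are used, and which power is meant (a given dose, or at least one dose). Report the result in Section 14.2 and, if it changes, in the synopsis power statement.

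The cost is one simulation re-run and two or three sentences, with no added patients. With the Holm step, the stated power for a given dose may come out below 80%.

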14.3 Analysis Sets

Safety Population and Intent-to-Treat Population (ITT) — all patients who received at least 1 injection of study medication.

Per Protocol Population (PP) — all patients who received at least 20 doses of study drug as assigned, completed the EOT Visit 26/Week 25, and had no major protocol violations that would potentially influence treatment effect (as determined by review by Idera prior to unblinding).

Safety analyses will be performed using the Safety Population. The efficacy, PD, disease-specific autoantibody, and immunogenicity assessments will be analyzed for the ITT population; key endpoints may be also analyzed for the PP Population as specified in the Statistical Analysis Plan (SAP). Analyses will be performed comparing the IMO-8400 treatment groups with placebo. Details will be provided in the SAP.

14.4 Statistical Analyses

14.4.1 Demographic and Baseline Characteristics

Patient demographics and baseline characteristics will be summarized descriptively by treatment group.

14.4.2 Study Conduct and Patient Disposition

The number of patients who enrolled in the study, the number randomized to each group, and the number in each analysis set will be summarized descriptively. The number of patients who completed the study will be summarized, and for those who terminated study participation before study completion, the reason for early termination will be tabulated by treatment group.

14.4.3 Treatment Compliance

Study drug exposure will be tabulated by the number of doses of study drug received. The number of and reason for missed doses will be tabulated categorically by treatment group.

14.4.4 Efficacy Analyses

The primary efficacy endpoint will be assessed via an RMMM. An appropriate covariance structure for repeated measures will be used. The difference between each IMO-8400 treatment group and placebo at Week 25 will be assessed. The overall alpha level will be controlled using the Bonferroni-Holm step-down method. Further details of this analysis will be described in the SAP. A sensitivity analysis will be performed to test the effect of important covariates on the effect of IMO-8400 using an RMMM.

Differences in response rate between the IMO-8400 treatment groups and placebo will be assessed via logistic regression.

The MMT8, TUG, 4 stair climb test, timed 10MWR test, serum CK, ALD, LDH, AST, ALT, SF-36, and 5-D Itch Scale will be analyzed in a similar manner to the primary endpoint.

For the proportion of patients who meet the IMACS 2004 DOI (Rider 2004) at EOT, logistic regression will be performed.

All efficacy endpoints will also be summarized descriptively by treatment group and nominal visit. Other exploratory and sensitivity analyses will be specified in the SAP in addition to further details regarding the statistical methodology.

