8.4.1.2 Randomization

Randomization will take place using IXRS. Patients will be randomized after the Investigator has verified that they are eligible per criteria in Section 7. Patients will be randomized to receive either IMO-8400 at a dose of 0.6 or 1.8 mg/kg/week or placebo once a week for 24 weeks. Randomization will be performed centrally in a 1:1:1 ratio and will be stratified by baseline CDASIV2-Activity score (15 to 20 vs ≥ 21). A permuted block randomization schedule will be employed. Blocks will be pre-allocated to the two CDASIV2-Activity strata (15 to 20 vs. ≥ 21) to achieve a balanced distribution of treatment assignments within those groups.

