14.5 Significance Levels

Statistical analyses will use a 1-sided test with alpha set at 0.05.

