17.2.1 Baseline Disease Activity Assessment

Baseline CDASI is likely to have prognostic significance for the primary assessment of skin activity. Changes in CDASI over 12 and 24 weeks for a convenience sample of 115 patients were analyzed by baseline score (unpublished data). Approximately 30% of patients showed improvement in CDASI scores by at least 4 points (clinically relevant changes) at both the 12- and 24-week assessment. Improvements are assumed to result from current standard care, although no data on treatments during the 24 weeks were collected. Patients with a high baseline CDASI score experienced larger decreases in CDASI at 24 weeks than those with a low baseline score. To control for possible effects of baseline disease activity on the results, randomization will be stratified by baseline CDASIV2-Activity score (15-20 vs. ≥ 21), and the study will be powered to detect a 7 point treatment effect, a therapeutic effect beyond that of the standard of care.

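### Does the primary repeated measures model leave out baseline score and randomisation stratum, and so give away power?

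*Protocol*

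**What the plan says.** Section 14.4.4 and the Synopsis describe the primary efficacy analysis by its method (an RMMM), a covariance structure to be chosen as appropriate, and the contrast of each IMO-8400 group with placebo at Week 25. On multiplicity the section says "The overall alpha level will be controlled using the Bonferroni-Holm step-down method", and Section 14.5 adds "Statistical analyses will use a 1-sided test with alpha set at 0.05". No fixed effects are listed. The section states that the SAP will give further details of this analysis, and at its end it again refers methodological detail to the SAP.

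The only mention of covariates is "A sensitivity analysis will be performed to test the effect of important covariates on the effect of IMO-8400 using an RMMM". None is named.

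Baseline activity appears in three other places:

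- Section 8.4.1.2: "Randomization will be performed centrally in a 1:1:1 ratio and will be stratified by baseline CDASIV2-Activity score", with strata 15 to 20 and 21 or more.
- Section 17.2.1: "Baseline CDASI is likely to have prognostic significance for the primary assessment of skin activity". The same section reports larger 24-week decreases in patients with high baseline scores, and gives stratified randomisation as the means of controlling for baseline activity.
- Section 14.2: the correlation between baseline and Week 25 scores "was assumed to be 0.4 for IMO-8400 treated patients and 0.7 for placebo treated patients".

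**The concern.** Taken together, these passages can suggest a gap. The endpoint is a change score, the primary model is described without baseline or stratum, and the word covariates occurs only under a sensitivity analysis. A reader may conclude that the primary test is unadjusted.

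That would matter. A plain change score fixes the slope of Week 25 on baseline at 1. Under the Section 14.2 correlations, and with equal SDs at both times, the average slope is (0.4 + 0.7)/2 = 0.55. Each point of baseline difference between arms would then shift the unadjusted contrast by about 1 − 0.55 = 0.45 points. With 10 to 12 patients per arm and two broad strata, some imbalance within strata is likely. Omitting the stratification factor from the model also leaves its variance in the residual. The more precise estimate would exist only as a sensitivity result.

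**Working it through.** **Inputs (Section 14.2 unless noted).** Effect: "one of the IMO-8400 groups exhibits a mean decrease of 7 points in CDASIV2-Activity score over 24 weeks". Spread and placebo response: "assuming a baseline mean of 25 and a standard deviation of 8.5 and the placebo group exhibits no mean decrease". Correlations: 0.4 (IMO-8400) and 0.7 (placebo). The 10 patients with complete data are read as 10 per group, because the final size is 12 per group. One-sided alpha is 0.05 (Section 14.5), and the first Holm step for two comparisons is 0.05/2 = 0.025. The SD of 8.5 is assumed to hold at Week 25 as well as at baseline, so SD² = 72.25.

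**Step 1: the plan's own power figure.** Section 14.2 reports 81.2% from a simulation of monthly assessments. By the normal approximation that needs 7/SE = 1.645 + 0.885 = 2.530, so SE = 2.767. The correlation between intermediate visits, the time trend and the fixed effects used are not stated, so several models were tried:

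| Model for the Week 25 contrast | SE | Power |
|---|---|---|
| Visit categorical, unadjusted change | 3.606 | 61.6% |
| Visit categorical, baseline as a response with common mean | 3.175 | 71.2% |
| Linear time, equal visit correlations, separate baselines | 2.891 | 78.1% |
| Linear time, equal visit correlations, common baseline | 2.601 | 85.2% |
| Linear time, correlation decaying with time, separate baselines | 3.606 | 61.7% |
| Linear time, correlation decaying with time, common baseline | 3.171 | 71.3% |

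None gives 81.2%. The figure is therefore not reproduced. It is not shown to be wrong either, since it lies inside the range and depends on unstated settings. It does not reveal whether the simulated model adjusted for baseline.

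**Step 2: what an unadjusted contrast would cost.** The variance of change in one arm is 2 × SD² × (1 − r).

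- IMO-8400: 2 × 72.25 × 0.6 = 86.70
- Placebo: 2 × 72.25 × 0.3 = 43.35
- Sum 130.05; SE = √(130.05/10) = 3.606

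With baseline as a covariate and common slope b = 0.55, the variance is SD² × (1 + b² − 2br).

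- IMO-8400: 72.25 × (1 + 0.3025 − 0.44) = 62.32
- Placebo: 72.25 × (1 + 0.3025 − 0.77) = 38.47
- Sum 100.79; SE = √(100.79/10) = 3.175

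The variance ratio is 100.79/130.05 = 0.775, so residual variance is 22.5% lower.

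Power by the normal approximation, Φ(7/SE − z):

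| n per group | One-sided alpha | Unadjusted | Adjusted |
|---|---|---|---|
| 10 | 0.05 | 61.6% | 71.2% |
| 10 | 0.025 | 49.2% | 59.7% |
| 12 | 0.05 | 68.5% | 78.0% |
| 12 | 0.025 | 56.6% | 67.6% |

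At n = 10 and alpha 0.05, the noncentral t gives 58.8% against about 68%, and simulation gives 59.1% against about 66.5%. Within any one method the gain there is about 7 to 10 points. Any further gain from the stratum cannot be computed, because the protocol does not give the split between strata.

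**Step 3: does the text make the unadjusted contrast the planned test?**

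- Section 14.4.4 cannot be a complete list of model terms. The Week 25 contrast between groups needs treatment and visit in the model, and neither is listed as a term. Reading the absence of baseline as exclusion would exclude these too.
- The sensitivity sentence concerns how covariates bear on the treatment effect. It names neither baseline nor stratum. If the SAP put both in the primary model and tested other covariates afterwards, the sentence would stand unchanged.
- Sections 8.4.1.2 and 17.2.1 make baseline a stratifier and call it likely prognostic. Neither says that the analysis ignores it.
- A baseline covariate is not the only route to the gain. The second row of the Step 1 table obtains SE 3.175 by treating baseline as a response with a common mean, and nothing in the protocol rules that out.

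**The case for a change.** The strongest reply is that the protocol is not merely silent. It gives covariates a role, and that role is a sensitivity analysis. Section 17.2.1 names stratified randomisation as the control for baseline activity and says nothing of model adjustment, so an unadjusted primary model is one natural reading. Stating the terms would take one sentence, use data already collected, and remove any later choice between adjusted and unadjusted results.

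Part of this stands. Adjusting for a prognostic stratification factor is good practice, the protocol could have said so, and the arithmetic in Step 2 is right for an unadjusted test. But the objection turns a possible reading into a stated one. The covariates in the sensitivity analysis are unnamed, and the section twice refers detail to the SAP. Choosing the fixed effects of a mixed model is what a protocol commonly leaves there.

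**Conclusion.** The concern does not hold. The protocol does not exclude baseline score or stratum from the primary RMMM. It leaves the model terms to a SAP that is not at hand, and the sensitivity sentence fits an adjusted primary model as well as an unadjusted one. The figures of about 22% of residual variance and about 7 to 10 points of power (n = 10 per group, one-sided 0.05) are conditional. They require that the primary test be a single-visit, unadjusted change contrast, that the SD be 8.5 at both times, and that the Section 14.2 correlations apply. The first condition is stated nowhere. No loss against the planned 81.2% is shown either, since that figure lies above both the unadjusted 61.6% and the adjusted 71.2% and rests on simulation settings that are not given.
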